### Design and Outcomes

This is a randomized, parallel-group phase II study to assess EVPOME vs. POM to determine differences in the primary efficacy measure of increased keratinized mucosa; secondary measures of graft contracture and Wound Healing Index; and ancillary outcome measures of tissue perfusion measured graft color and laser Doppler flowmetry, and postoperative pain.

Primary outcome measure: Clinical increase in zone (width) of keratinized mucosa (KM). For edentulous sites, KM width will be measured by determining the distance from the crest of the edentulous ridge to the mucogingival line to the nearest millimeter with a Castroviejo caliper. For patients with an existing implant, KM width will be measured from the implant mucosal margin to the mucogingival line. The amount of attached gingival tissue (keratinized) will be evaluated using a calibrated periodontal probe measured to nearest 0.5mm.

Secondary outcome measures: Graft contracture will be measured in mesio-distal and corono-apical directions. Post-surgical measurements of the graft site will be taken at visits 5, 6, 7, and 8, and will be compared to the original graft size to assess percentage of graft contracture. Wound Healing Index (WHI) will be recorded after surgery using the following criteria:

- Score 1= uneventful healing with no gingival edema, erythema, suppuration, patient discomfort, or flap dehiscence
- Score 2 = uneventful healing with slight gingival edema, erythema, patient discomfort, or flap dehiscence, but no suppuration
- Score 3 = poor wound healing with significant gingival edema, erythema, patient discomfort, flap dehiscence, or any suppuration

Ancillary outcome measures: Laser Doppler flowmetry (LDF) measurements will be used

to assess graft blood flow (tissue perfusion of the grafts).

Graft color is correlated to vascular perfusion and thus can give us an indication of graft vascularity. Finger pressure will be applied in the center of the graft for 15 seconds and/or until tissue blanching. The pressure will then be released and the time for the tissue to return to its previous color will be recorded. If the tissue returns to its previous color within 15 seconds, this will be recorded as positive graft vascularity. If not, then it will be recorded as negative graft vascularity.

Overall postoperative pain will be assessed via a visual analog scale (VAS).

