## 9.2 Outcomes

### 9.2.1 Primary outcome

The primary outcome will be clinical increase in zone (width) of keratinized mucosa (KM). For edentulous sites, KM width will be measured by determining the distance from the crest of the edentulous ridge to the mucogingival line to the nearest millimeter with a Castroviejo caliper. For patients with an existing implant or tooth, KM width will be measured from the implant mucosal or tooth margin to the mucogingival line.

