### 9.3 Sample Size and Accrual

We propose to have 60 subjects to give clinical and histological endpoints of interest at the primary assessment time of 4 weeks post graft. We expect no more than 6 subjects to potentially drop out of the study before providing Week 4 data, and thus will enroll 66 patients in total. With an estimated enrollment of 1 out of 5 screened patients, we expect to have a pool of over 330 patients over two years from which to select 66 subjects (33 subjects per group over two years) that will be randomized equally to one of the two groups - EVPOME and POM grafts. The randomization list will be prepared electronically in advance by the biostatistician and transferred to the MICHR statistics group for incorporation into the TATUM system. Randomization will be stratified by smoking status.

The primary clinical endpoint is the degrees of keratinized tissue. Secondary outcomes are contracture and wound healing index. Ancillary endpoints include the presence or absence of a continuous epithelial layer, the degree of vascular ingrowth, the LDF measurement of gingival blood flow. The main aim is to show that EVPOME treatment give comparable clinical and histological results when compared with POM treatment. It is also expected that the EVPOME will cause less patient discomfort and pain, and have a better color rendition to the surrounding tissue than the POM. Hence, we expect EVPOME to show better outcomes for pain, color rendition, and microvessel infiltration than POM, while showing comparable outcomes on primary endpoints of keratinized tissue and graft contracture or histological endpoints compared with POM. Sample size is calculated to show near equivalence of the two groups for primary and secondary outcomes. Sample size calculation and power consideration are provided following the data analytic plan described for each outcome.

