## 9.5 Data Analyses

The main aim of the study is to determine by quantitative outcome measures that EVPOME will function as well as POM in terms of increased epithelialized tissue, decreased contracture, and increased microvessel infiltration. It is also expected that the EVPOME will have a closer adaptation in color rendition to the surrounding tissue. Our primary comparisons will be based on the observations at four weeks post-graft.

**AIM 1 - Keratinized Tissue:** Primary comparison will be based on week 4 assessment using an equivalence test of means. Background data on measurements of keratinized tissue for POM (standard of care) gave a mean measurement of 3.70 mm with an SD of 0.65 mm. The mean and SD were relatively constant over the follow up period from 3 to 12 months. If, in this study, both EVPOME and POM give comparable results, the distribution of the mean difference in keratinized tissue with 30 subjects in each arm will be approximately normal with a mean of 0 and standard error of 0.17, and a 95% confidence interval for the true mean difference between the two procedures will have a margin of error of about 0.33 mm. This confidence interval will exclude a value for the mean difference of 0.55mm or larger with probability at least 80%. Therefore sample size will be adequate to show near equivalence of the two treatments if the degree of keratinized tissue measurement of EVPOME is within  $\pm 0.55$ mm of POM. Statistical power will be even larger if non-inferiority of EVPOME to POM is desired, where true increase in keratinized zone in EVPOME group is no less than 0.55 mm compared with the increase of zone of keratinized tissue in POM.

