**Laser Doppler Flow (LDF):** LDF data will be compared based on gingival blood flow at Week 4 post-surgery at the graft site between the EVPOME and POM groups. One aspect of this study will be to examine and explore the usefulness of this measure. In particular, we will explore the use of control measures taken on normal tissue to help adjust for intra subject factors contributing to the variability. The primary investigation will compare gingival blood flow at the graft site at two weeks, four weeks, eight weeks, and 24 weeks post-surgery to the values in an analysis of covariance (ANCOVA) model. The corresponding differences at the control site will also be incorporated as a covariate to partially adjust for intra-individual variability. More detailed analyses will utilize ANCOVA methods for repeated measures. There is relatively little background data on the use of LDF to measure perfusion in the context being studied here though some preliminary data on measuring gingival blood flow can be found in Justus et al. where change in gingival blood flow from baseline to post surgery (over the period 7 to 24 .days) was found to have a mean of about -25 perfusion units (PU) with an SD of about 60 PU. The measurement is highly variable.

For repeatedly measured data such as pain and wound healing index, data will be

summarized by treatment groups at each follow-up time. In addition, linear mixed-effects models will be used to make the between group comparison while adjusting for potential within person correlation of the outcome variables. By using the modeling approach, it will be possible to incorporate all observations from both treatment groups and make between treatment group comparisons efficiently using a treatment dummy indicator. The model will allow us to not only compare the time-averaged means, but also allows us to explore the rate of decline between the EVPOME and POM groups such as the rate of decline in pain, using appropriate interactions terms. When appropriate, comparisons between treatments will be adjusted for surface area of the graft as well as measures of its geometry, and other variables including age, general health and alcohol use.

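### AIM 1 does not say whether keratinized-mucosa width or its increase is tested at Week 4; ANCOVA on baseline width is a cheap improvement that settles this for about one point of power at worst

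*Combined protocol and SAP*

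**What the plan says.** Outcome. Section 9.2.1 states: "The primary outcome will be clinical increase in zone (width) of keratinized mucosa (KM"). The Synopsis agrees. Section 9.3 words it differently: "The primary clinical endpoint is the degrees of keratinized tissue".

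Test. Section 9.5, AIM 1: "Primary comparison will be based on week 4 assessment using an equivalence test of means". It does not say whether the means are of width or of increase.

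Planning SD. The POM background data "gave a mean measurement of 3.70 mm with an SD of 0.65 mm". Also: "The mean and SD were relatively constant over the follow up period from 3 to 12 months". No SD is given for the engineered graft (EVPOME) and no KM SD for Week 4. AIM 2, by contrast, cites a 4-week SD for contracture.

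Power. "This confidence interval will exclude a value for the mean difference of 0.55mm or larger with probability at least 80" per cent, with 30 subjects per arm and a true difference of 0. AIM 1 frames equivalence in terms of the tissue measurement, and non-inferiority in terms of the increase. The same 0.55 mm and 0.65 mm serve both.

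Covariates. Later in Section 9.5: "When appropriate, comparisons between treatments will be adjusted for surface area of the graft as well as measures of its geometry", followed by age, general health and alcohol use. Baseline KM is neither named nor excluded.

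Baseline reading. Section 6.1 ticks clinic assessments at Visit 1, but its footnote makes keratinization an optional item. Section 6.3.5 lists KM width only for Visits 5 to 8. Eligibility (4.1.2) requires KM of 3 mm or less, so a reading is needed at screening.

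**The concern.** A width and an increase in width can have different SDs, and the plan applies one SD to both without saying which it describes. The SD also comes from month 3 onward, while the primary comparison is at Week 4. The calculation has little slack: exactly 80% power needs an SD of at most 0.657 mm (normal) or 0.646 mm (t).

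Leaving the scale open has two consequences. Power for the test actually run could lie below or above the stated figure, depending on a baseline SD and a correlation that the documents do not give. And the choice between width and increase could be made after the data are seen, in a trial whose conclusion depends on a confidence interval falling inside a fixed margin. Baseline adjustment removes the choice, but it needs a baseline value that the schedule does not firmly require.

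**Working it through.** **Inputs from Section 9.5, AIM 1:** SD 0.65 mm, 30 per arm, margin ±0.55 mm, two-sided 95% CI, true difference 0. **Assumed:** baseline SD s_b and baseline-to-Week-4 correlation r (the documents give neither), and illustrative SDs of 0.70 and 0.75 mm.

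**1. The plan's own figure.** SE = 0.65 × √(2/30) = 0.168; 1.96 × SE = 0.33 mm, as stated. Power = 2Φ(0.55/0.168 − 1.96) − 1 = 2Φ(1.317) − 1 = 81.2%. With the t distribution (58 df, averaged over the sample variance) it is 79.3%. The stated 80% reproduces, for any variable whose SD is 0.65 mm.

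**2. Unadjusted test at other SDs (t):** 70% at 0.70 mm, 60% at 0.75 mm.

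**3. If 0.65 mm is the width SD and the simple increase is tested.** SD of increase = √(0.65² + s_b² − 2 × r × 0.65 × s_b).

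| s_b (assumed) | r = 0.3: SD, power | r = 0.5: SD, power |
|---|---|---|
| 0.30 | 0.629, 83% | 0.563, 92% |
| 0.50 | 0.691, 72% | 0.589, 89% |
| 0.65 | 0.769, 56% | 0.650, 79% |

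The reverse mismatch behaves alike. If 0.65 mm is the SD of the increase and unadjusted width is tested, width SD = r·s_b + √((r·s_b)² − s_b² + 0.65²). Power is 75% at s_b 0.3, r 0.3 (SD 0.674) and 63% at s_b 0.5, r 0.5 (SD 0.735).

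**4. ANCOVA of Week 4 width on baseline width.** Subtracting baseline from the response changes only the baseline coefficient, by exactly 1, so the adjusted treatment difference is identical for width and for increase. The residual SD is the minimum over b of SD(width − b × baseline). Since b = 0 gives the width and b = 1 gives the increase, it cannot exceed either SD.

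Power uses 57 df, with the variance of the difference multiplied by 1 + 1/56 for the covariate.

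- If 0.65 mm is the Week 4 width SD, residual SD = 0.65 × √(1 − r²). Power is 78.2% at r = 0 (0.650), 83% at r = 0.3 (0.620) and 92% at r = 0.5 (0.563), against 79.3% unadjusted. ANCOVA overtakes the unadjusted width test at r of about 0.13.
- If 0.65 mm is the SD of the increase, the floor is again 78.2%, reached when the baseline slope is 1.

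**5. What the floor depends on.** Each line changes one condition, with no help from baseline.

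- Week 4 SD 0.70 or 0.75 mm in both arms: about 69% or 58%.
- 27 evaluable per arm: 71%.
- True difference 0.1 mm (assumed): 71%.
- EVPOME SD 0.75 mm with POM 0.65 mm (assumed; root-mean-square 0.702): 68%.

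**The case against.** The strongest reply is that nothing here is shown to be an error. The 80% reproduces, AIM 1 implicitly applies 0.65 mm to Week 4, and one sentence labelling the SD would close the documentary gap. Under randomization, unadjusted width and unadjusted increase have the same expected difference between arms, so neither test aims at the wrong effect. AIM 1's non-inferiority sentence already points to the increase. No correlation is documented, and enrolling only sites with KM of 3 mm or less may restrict baseline spread and weaken it. The low-power cells in step 3 rest on assumed values, and the same grid reaches 92%.

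Most of this stands. A reader might infer that the trial is underpowered, or that AIM 1 tests the wrong quantity. The documents support neither. What survives is that width and increase may differ in SD, the plan does not choose between them, and baseline adjustment removes the need to choose. The covariate sentence could admit baseline KM, but a covariate included only when judged appropriate does not prespecify the primary analysis.

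**Conclusion.** This is a cheap improvement, not a demonstrated fault. AIM 1 should name the quantity tested and adjust for baseline KM.

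If the SD is 0.65 mm at Week 4 in both arms, with 30 evaluable per arm and a true difference of 0, ANCOVA keeps at least about 78% power whether 0.65 mm is a width SD or a gain SD. On the width reading it gains about 4 points over the unadjusted test at r = 0.3 and about 12 at r = 0.5.

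It is tempting to read the 78% as a guarantee. It is not: ANCOVA resolves width versus increase but says nothing about variability at Week 4 or in the EVPOME arm. The number of evaluable subjects is also unsettled, because the Synopsis and Section 3 randomize 60 while Section 9.3 enrols 66 to allow for 6 dropouts.

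**What to change.** 1. In Section 9.5, AIM 1, write: *Week 4 KM width is analysed by ANCOVA with treatment and baseline (Visit 1) KM width; equivalence is concluded if the 95% CI for the adjusted EVPOME minus POM difference lies within −0.55 to +0.55 mm.* Add that this difference is the same for width and for increase.
2. In Section 6.1, make KM width a required recorded value at Visit 1. In Section 6.3.5, add Visit 1 to the visits at which KM width is assessed.
3. State whether 3.70/0.65 mm is a width or a gain, and that the 80% assumes this SD at Week 4 in both arms. Show power at 0.70 and 0.75 mm.

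If ANCOVA is not adopted, item 3 is still needed, and AIM 1 should state whether width or increase is tested. The baseline value remains necessary, because an increase cannot be computed without it.

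Cost: wording in three sections, one degree of freedom, and about one point of power (79% to 78%) if baseline and Week 4 widths are uncorrelated. No added visits or subjects.

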**AIM 2 - Shrinkage in Graft:** The percent shrinkage (contracture) in graft will be expressed as  $100*(1 - (\text{Area final}/\text{Area Day0}))$ , and the comparison will be based on week 4 assessment using an equivalence test of means (with log transformation if the data are highly skewed upon visualization). Prior data for POM gave a mean shrinkage of 25% at 4 weeks post-op with a standard deviation (SD) of about 13%. If shrinkage is about the same for both EVPOME and POM, with a sample size of 30 subjects in each group, this translates into an estimate of the mean difference with standard error of about 3.4%. This gives a margin of error of 6.6% for a 95% confidence interval, and the 95% confidence interval excluding a value for the mean difference in shrinkage as large as 11% with probability of 80%.

**Wound Healing Index (WHI):** WHI will be analyzed via the following chart, and the index will be tabulated by treatment group at follow-up visits 5, 6, 7, and 8. Depending on the observed distribution of the index, the data will either be dichotomized or considered as an ordinal data.

Scores	Criteria
1	Uneventful healing with no gingival edema, erythema, suppuration, patient discomfort, or flap dehiscence
2	Uneventful healing with slight gingival edema, erythema, patient discomfort, or flap dehiscence but no suppuration

3	Poor wound healing with significant gingival edema, erythema, patient discomfort, flap dehiscence, or any suppuration
---	---

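### AIM 1's 80% power holds for a true difference of about zero, but its concluding sentence calls the sample adequate for any EVPOME-POM difference within ±0.55 mm

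*Combined protocol and SAP*

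**What the plan says.** Section 9.5, AIM 1 sets the primary test: "Primary comparison will be based on week 4 assessment using an equivalence test of means". Background data for POM "gave a mean measurement of 3.70 mm with an SD of 0.65 mm". The calculation opens with a condition, "If, in this study, both EVPOME and POM give comparable results", under which the mean difference with 30 per arm "will be approximately normal with a mean of 0 and standard error of 0.17". From this, "a 95% confidence interval for the true mean difference between the two procedures will have a margin of error of about 0.33 mm", and the interval is said to exclude a difference of 0.55 mm or more with probability of at least 80%.

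The conclusion follows: "sample size will be adequate to show near equivalence of the two treatments if the degree of keratinized tissue measurement of EVPOME is within" (the bound given is ±0.55 mm either side of POM). The next sentence adds: "Statistical power will be even larger if non-inferiority of EVPOME to POM is desired", and describes that case by the true EVPOME increase relative to POM, again using 0.55 mm.

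No power is given for any non-zero true difference. No other section names ±0.55 mm as the equivalence margin.

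**The concern.** Two quantities need to be kept apart: the margin that the confidence interval must stay inside, and the true difference assumed when power is computed. AIM 1 computes power at a true difference of 0 and then states adequacy as a condition on how far EVPOME lies from POM, using the margin as the bound. Taken at its word, the sentence promises adequate power for a graft that is truly 0.2, 0.3 or even 0.5 mm different, which the design does not provide.

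The sentence carries weight. Section 9.3 says that the sample size was calculated to show near equivalence and refers to the analytic plan for the justification, and for the primary outcome this is that justification. Section 1 says that the results will be used to plan a Phase III trial. A true difference of exactly 0 is also an assumption without direct support: the documents report no earlier comparison of EVPOME with POM, and Section 2.2 describes a Phase I study with no control group and a different scaffold.

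**Working it through.** **Inputs (Section 9.5, AIM 1).** SD 0.65 mm; 30 analysed per arm; margin 0.55 mm; equivalence shown when the two-sided 95% confidence interval lies wholly inside ±0.55 mm. That rule equals two one-sided tests at 2.5% each. AIM 1 states no other significance level.

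**Step 1: reproduce the plan's figures.**
- SE = 0.65 × √(2/30) = 0.1678 mm (plan: 0.17).
- Margin of error = 1.96 × 0.1678 = 0.329 mm (plan: about 0.33).
- To succeed, the observed difference must lie within ±(0.55 − 0.329) = ±0.221 mm.
- Power at a true difference of 0 = Φ(0.221/0.1678) − Φ(−0.221/0.1678) = 0.906 − 0.094 = 81.2%.
- With the rounded SE of 0.17 the result is 79.8%; with the exact t distribution (58 df) it is 79.3%.

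The stated 80% therefore reproduces, for a true difference of 0.

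**Step 2: move the true difference d away from 0.**
- Equivalence power(d) = Φ((0.221 − d)/0.1678) − Φ((−0.221 − d)/0.1678).
- Non-inferiority power (one-sided 2.5%, EVPOME worse by d) = Φ((0.221 − d)/0.1678).

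For example, at d = 0.2 mm equivalence power is Φ(0.125) − Φ(−2.51) = 0.550 − 0.006 = 54.4%.

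| True difference (mm) | Equivalence, normal | Equivalence, exact t | Non-inferiority, normal, EVPOME worse |
|---|---|---|---|
| 0 | 81% | 79% | 91% |
| 0.1 | 74% | 72% | 76% |
| 0.2 | 54% | 53% | 55% |
| 0.3 | 32% | 31% | 32% |
| 0.4 | 14% | 14% | 14% |
| 0.5 | 5% | 5% | 5% |
| 0.55 | 2.5% | 2.5% | 2.5% |

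By the normal approximation, equivalence power stays at or above 80% only up to a true difference of about 0.04 mm.

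**Step 3: non-inferiority when EVPOME is better.** If EVPOME is truly 0.2 mm better, non-inferiority power is Φ((0.221 + 0.2)/0.1678) = Φ(2.51) = 99%, against 54% for equivalence.

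**Step 4: sensitivity to the interval.** With a 90% interval, which AIM 1 does not specify, equivalence power would be 90% at 0, 67% at 0.2 mm and 9% at 0.5 mm, with 80% kept up to about 0.13 mm. The conclusion is the same.

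**The case against.** The best defence is that the concluding sentence only names the margin. The zero-difference premise is stated openly a few lines earlier and can be taken to carry forward, and nowhere does the plan claim 80% power at 0.2 or 0.5 mm. Under Histological Epithelial Coverage in the same section, the assumed true proportion (75%) and the tolerated difference (36.5%) are kept apart, so the authors know the distinction.

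This reading is possible, but the words are against it. The sentence sets a condition on the EVPOME measurement, the next one speaks of the true increase, and no other text identifies ±0.55 mm as the margin. The defence does rule out several stronger conclusions that a reader might draw:

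- **That the arithmetic or the sample size is wrong.** It is not: SE, margin of error and 80% all reproduce. Powering an equivalence test at a stated zero difference is a legitimate choice, and the fall to 2.5% at the margin is true of any such test at this level.
- **That the claim of larger non-inferiority power is false.** It is true. Non-inferiority power is never below equivalence power by the formulas above (91% against 81% at 0). The gain becomes negligible from about 0.2 mm only when EVPOME is worse; when EVPOME is better it is large. What needs correcting is the clause that puts 0.55 mm in the place of the true difference.
- **That AIM 2 has the same fault.** It does not. It assumes that shrinkage is about the same in both groups and reports "the 95% confidence interval excluding a value for the mean difference in shrinkage as large as 11% with probability of 80"%. It has no sentence making adequacy depend on lying within the margin.
- **That a failed test would be taken to show that the grafts differ.** No section says so.

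**Conclusion.** Wrong as written: a mistaken conclusion drawn from a correct calculation. AIM 1 presents ±0.55 mm as the range of differences over which the sample is adequate, whereas about 80% power exists only for a true difference very close to 0. A graft truly 0.2 to 0.3 mm different, well inside the margin, would fail to show equivalence in about 46% to 68% of trials (100 − 54.4 and 100 − 31.8).

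These figures rest on the plan's SD of 0.65 mm in both arms, 30 evaluable subjects per arm, approximate normality, and the 95% interval as the decision rule. Normal and exact t results differ by no more than about 2 percentage points. The matter should be corrected because this sentence justifies the primary sample size, but it casts no doubt on the number of subjects, the margin or the planned test.

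**What to change.** In Section 9.5, AIM 1, replace the concluding sentence with:

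> The equivalence margin is ±0.55 mm. With 30 evaluable subjects per arm, the power to place the 95% confidence interval within this margin is about 81% if the true mean difference is 0; it falls to about 74% at 0.1 mm, 54% at 0.2 mm and 32% at 0.3 mm (normal approximation).

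Replace the non-inferiority sentence with:

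> For non-inferiority with a margin of 0.55 mm (one-sided 2.5% level), power is about 91% if the true mean difference is 0, about 55% if EVPOME is truly 0.2 mm worse, and higher than 91% if EVPOME is truly better (normal approximation).

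If the authors prefer exact t values for equivalence (79%, 72%, 53% and 31%), they should use t values throughout and not mix the two series. AIM 2 needs no change on this point.

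The cost is wording only: no added subjects or procedures, and no change to sample size, margin or analysis. The stated power becomes less favourable away from zero.

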## 9. STATISTICAL CONSIDERATIONS

### 9.1 General Design Issues

This is a randomized, parallel-group (autogenous *ex vivo* produced oral mucosa equivalent (EVPOME) vs. palatal oral mucosa (POM)) safety and efficacy study in subjects requiring additional keratinized oral mucosa for dental rehabilitation. The primary hypothesis is that EVPOME is an equivalent intraoral grafting material when compared to POM in regards to keratinized tissue and graft contracture, but is superior to POM in regards to pain, color rendition, and microvessel infiltration.

The comparison will be done using primary efficacy measures of enhanced keratinization, and secondary measures of graft contracture and wound healing index, and ancillary measures of increased microvessel ingrowth. Clinical assessments will include postoperative pain. Intraoral photographs will be done at screening and at biopsy, 2, 4, 8, and 24 weeks after intra-oral grafting. Tissue biopsy will be conducted at week 4 and laser Doppler flowmetry at weeks 2, 4, 8, and 24. Primary assessment time will be at week 4, and final assessments for all subjects will be at week 24.

Subjects will be screened until we have the necessary 60 enrolled. It is likely there will be 4 screened subjects to 1 enrolled subject. All subjects will undergo informed consent prior to any screening procedures. It is expected that it will take 2.5 years to successfully enroll 60 patients. Subjects will be recruited through the Patient Admitting and Emergency Services (PAES) clinic in the U-M School of Dentistry in conjunction with MCOHR. All new patients are routed through PAES and assigned to specialty or

undergraduate clinics. Most patients do not return to the PAES clinic, so we are not likely to have redundancy. PAES had 13,100 visits in 2003. It is estimated that 40% of the western population is missing 1 or more teeth (50% to be restored with implants for our purposes). Approximately 1/3 of them are in need of soft tissue oral mucosa grafts which is a very common procedure. This will give us a population from which to draw approximately 865 new patients per year. Of this group we need to recruit 60 subjects over two years from a potential pool of 1,730 patients. With an estimated enrollment of 1 out of 4 screened patients, we should have a pool of over 400 patients per year from which to select 30 subjects. Subjects will be recruited by full-time faculty members in the Department of Periodontics at the U-M School of Dentistry.

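### The Week 4 primary test is two-sided equivalence on an outcome where more is better; no reason is given for the upper limit, and one loose sentence adds non-inferiority

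*Combined protocol and SAP*

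**What the plan says.** Section 9.1 states the hypothesis: "The primary hypothesis is that EVPOME is an equivalent intraoral grafting material when compared to POM in regards to keratinized tissue and graft contracture". It claims superiority only for pain, color and microvessels. Section 9.3 sizes the trial for near equivalence on the primary and secondary outcomes.

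Section 9.5, Aim 1, names the test: "Primary comparison will be based on week 4 assessment using an equivalence test of means". The sizing uses a 95% confidence interval and a margin of 0.55 mm in either direction, with a probability of at least 80%. After that conclusion comes the remark "Statistical power will be even larger if non-inferiority of EVPOME to POM is desired", with the same 0.55 mm margin. The rest of that sentence, read literally, does not say that EVPOME may be at most 0.55 mm lower than POM.

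Aim 2 uses an equivalence test for percent contracture at Week 4, with a difference of 11 percentage points as the value to exclude.

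The desired direction appears elsewhere. Section 9.2.1 defines the primary outcome as an increase in the width of keratinized mucosa, and Section 4.1 admits subjects whose band is 3 mm or less. Section 9.5 opens with the aim of showing that "EVPOME will function as well as POM in terms of increased epithelialized tissue, decreased contracture, and increased microvessel infiltration".

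**The concern.** An equivalence test has two limits, and both must hold. The lower limit guards against a graft that gains too little keratinized mucosa, which is the clinical question. The upper limit makes the criterion fail when EVPOME gains clearly more. That is appropriate only if a larger gain is undesirable or would defeat the purpose of the claim, and no section says so. The same applies to Aim 2, where less contracture is the benefit.

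The non-inferiority remark adds to this. It gives no rule for when non-inferiority would apply or what role it would have. If the equivalence criterion were missed on the favorable side, the plan would not say how to read the result.

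The stakes are the power to reach the primary claim and a clear pre-specified reading of a favorable result. The false-positive rate for an inferior graft is not at stake.

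**Working it through.** **Inputs.** The SD comes from POM background data that "gave a mean measurement of 3.70 mm with an SD of 0.65 mm" (9.5, Aim 1). The sampling distribution is stated as "with 30 subjects in each arm will be approximately normal with a mean of 0 and standard error of 0.17". The margin is 0.55 mm with a two-sided 95% interval, i.e. 2.5% on each side. Aim 2 uses 30 per arm, SD 13 points and a margin of 11 points. Let d be the true difference, EVPOME minus POM, and Φ the standard normal distribution function.

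**1. The plan's own figure.** SE = 0.65 × √(2/30) = 0.168 mm. Margin of error = 1.96 × 0.168 = 0.329 mm, against the stated 0.33. Equivalence power at d = 0 is 2Φ(0.55/0.168 − 1.96) − 1 = 2Φ(1.317) − 1 = 2 × 0.906 − 1 = **81.2%**. With the SE rounded to 0.17 it is 79.8%, and a t-based simulation of 200,000 trials gives 79.3%. The stated figure of at least 80% is therefore reproduced, to within rounding, as two-sided equivalence.

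**2. What passes.** The interval lies inside ±0.55 mm only if the observed difference is within 0.55 − 0.329 = **±0.22 mm**. The interval excludes zero in EVPOME's favor only if the observed difference exceeds **0.33 mm**. At the planned SE the two regions do not overlap, so every statistically superior EVPOME result misses the equivalence criterion. For both to hold, the interval would have to fit between 0 and 0.55 mm. That needs a half-width below 0.275 mm, hence an SD below 0.275 / (1.96 × √(2/30)) ≈ 0.54 mm. A 90% interval would widen the passing range to ±0.27 mm, still short of 0.33.

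**3. Non-inferiority at the same n, margin and one-sided 2.5%.** Power = Φ((0.55 + d)/SE − 1.96). At d = 0 this is Φ(1.317) = **90.6%** (89.7% by t-based simulation), a gain of 90.6 − 81.2 = 9.4 points.

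**4. Illustration with EVPOME truly better.** Equivalence power = Φ((0.55 − d)/SE − 1.96) − Φ((−0.55 − d)/SE + 1.96). At d = 0.2 this is Φ(0.125) − Φ(−2.509) = 0.550 − 0.006 = 0.544.

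| True EVPOME advantage | Equivalence | Non-inferiority |
|---|---|---|
| 0 (plan's assumption) | 81.2% | 90.6% |
| 0.1 mm | 73.7% | 97.2% |
| 0.2 mm | 54.4% | 99.4% |
| 0.3 mm | 31.8% | 99.9% |

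Only the first row is the plan's scenario.

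**5. Aim 2.** SE = 13 × √(2/30) = 3.36 points. The margin-to-SD ratio is the same as in Aim 1 (11/13 = 0.55/0.65 = 0.846), so power at no difference is again 81.2% against 90.6%. If EVPOME truly shrank 6 points less (illustrative), equivalence would give Φ(5/3.36 − 1.96) − Φ(−17/3.36 + 1.96) ≈ 32%, and non-inferiority Φ(17/3.36 − 1.96) ≈ 99.9%.

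**The case against.** Equivalence looks like a deliberate choice. Sections 9.1, 9.3 and 9.5 agree on it, and they separate outcomes expected to be comparable from those expected to be better. For epithelial coverage, Section 9.5 sets out a directional non-inferiority comparison at a one-sided 97.5% level, so the authors could write one when they meant it. No stated figure is wrong, and the remark that non-inferiority has more power is true. The aim sentence also covers microvessels, for which Section 9.1 claims superiority, so its wording alone cannot fix the direction of the test.

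Most of this stands, and it rules out some stronger readings. A reader might infer that the primary test is undefined and free to be picked after the data are seen. The documents do not support that: equivalence is named consistently, and the non-inferiority sentence is a remark on power. A reader might also infer inflated type I error. There is none against inferiority, because both tests share the same lower limit at 2.5%.

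What the objection does not supply is a reason for the upper limit. The outcome is defined as an increase, in subjects chosen for a deficient band, and the plan's own treatment of epithelial coverage shows that a one-sided rule fits its logic.

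**Conclusion.** The point holds as a mismatch between the primary decision rule and the desired direction of the outcome, together with one sentence that needs resolving. The firm results are these: at the planned SE, any statistically superior EVPOME result misses the primary criterion; and under the plan's own assumption of no difference, the two-sided rule costs about 9 points of power (81.2% against 90.6%).

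The larger gaps, such as 54% against 99.4% at 0.2 mm, are illustrations. The documents give no expected EVPOME advantage, so these gaps should not be read as a forecast. Nor does missing equivalence amount to rejecting the graft, as a reader might infer: it means only that equivalence was not shown. The confidence interval would still display the benefit, and no section makes equivalence a condition for proceeding to Phase III.

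The figures assume normality and an SD of 0.65 mm in both arms at Week 4. The quoted SD describes a keratinized tissue measurement for POM over 3 to 12 months, whereas the outcome is the increase.

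**What to change.** Before data are seen, revise Sections 9.1 and 9.5:

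- Make the primary test non-inferiority for Week 4 keratinized mucosa: the lower limit of the two-sided 95% interval for EVPOME minus POM must be above −0.55 mm.
- If that holds, claim equivalence when the upper limit is also below +0.55 mm. In this fixed order the second claim costs no alpha, since equivalence is nested within non-inferiority.
- Apply the same order to contracture: first the upper limit of the difference in percent shrinkage (EVPOME minus POM) below +11 points, then equivalence if the lower limit is above −11.
- Delete the conditional remark on non-inferiority, and reword the clause that follows it so that it plainly says EVPOME may be at most 0.55 mm lower.

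The cost is wording only. No subjects are added: 30 per arm already gives 90.6% power for non-inferiority. The small downside is that the headline claim is non-inferiority unless both limits hold.

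If the sponsor does intend two-sided equivalence, it can keep it. The plan should then state why a larger gain does not meet the aim and remove the non-inferiority sentence.
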